10.1.2 Secondary endpoints

Normal Liver function test and renal function test should be taken as success end point towards safety.

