The investigational drug is a polyherbal Siddha formulation. It is proven as an anti-diabetic^{3, 4, 6}. Some studies have investigated the possible anti-diabetic properties of combination drug in animal models, one in a high fructose diet induced and another in alloxan diabetic rats^{3, 5}. The results of these studies show that the administration of the extracts reduced the blood sugar level. Gallic acid is the component present in the composition of investigational drug having anti-diabetic activity⁷. More over the same studies highlighted the anti-oxidant and anti-obesity effects of this drug. These effects are assumed to play a major role to reduce the chances of transition of IGT patients to established diabetics. According to ICMR-INDIAB study conducted

in 2011, 3.9 million are estimated to be in the state of prediabetes in Tamil Nadu. Projections for the whole of India would be 77.2 million pre-diabetic patients¹⁰. So a poly-herbal formulation which is more effective, cost effective and safety among prediabetes patients.

According to the above references life style modification is done holistically in this study with the study drug.

2. Clinical Study Objectives:

2.1 Primary objective:

To assess the efficacy of Siddha formulation in the individuals having Impaired Glucose Tolerance (IGT) – (Munneerizhivu). If, during treatment or after treatment OGTT 2 hours remain between 126 mg/dl and 140 mg/dl, fasting blood sugar between 70 mg/dl and 100 mg/dl and HbA1c is $\leq 6.0\%$ it will be treated as successful outcome of the treatment.

2.2 Secondary objective:

To determine the Toxicological data of Siddha formulation

[figure not shown]
3 Study Design:

Open labelled Randomized Controlled Clinical Trial.

There will be two arms in this study. To one group is assigned life style modification and test drug and to the other group Life Style Modification (LSM). Randomization will be achieved through Random numbers.

3.1 Allocation to treatment:

The subjects will be allocated to the drug interventional group and LSM group based on the Random numbers generated by the computer.

Schematic representation of Study Design

5 Criteria for Inclusion:

Subjects in their 3rd to 6th decade only will be included in this study. Subjects falling in any one of the following criteria i.e. 2 hours OGTT should be between 140 mg and 199 mg. Glycated hemoglobin (HbA1C) > 6.0% and <6.5% and Blood sugar – Fasting > 100 and =< 125 mg/dl will be included.

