5.1 Criteria for Exclusion:

Subjects with age below 30 and above 60 years are excluded in the study. The subjects are excluded in the study those who are known Diabetes, Malignant and accelerated hypertensive, Chronic Liver and Renal diseases, Coronary artery disease, Secondary Diabetes mellitus, CNS disorder (e.g. encephalopathy) and patient undergoing regular treatment for any other severe illness. Pregnant woman and planning to be pregnant within six months and lactating mother are excluded.

6. Study Drug:

The intervention group receives either trial drug or life style modification. The trial drug is an official Siddha formulation mentioned in Siddha Formulary. Recent animal studies have also proved its anti-diabetic activity. It is a kayakalpa drug having anti-oxidant potential, hypothetically assumed to act in IGT.

Dose: 500 mg Tablet , 4 tablets twice a day. Dose as per the market availability and the dose 4 gm / day is as per Marundhu Alavu Attavanai mentioned in Gunapadam Thatthu Jeeva Vaguppu.

The LSM group will be advised to adopt life style modifications (balanced diet along with brisk walking not less than 150 min/week.) These interventions will be measured via LSM intervention compliance form.

Duration of the medication: 180 days. Duration is to measure the range of HbA1c.

6.1 Study drug Compliance/Adherence:

The container will be checked and the tablets will be counted by which compliance will be checked during each and every visit. It can also be assessed based on the drug compliance

form (Form IV A) for drug intervention group. The LSM group can be assessed based on the LSM intervention compliance form (Form IV B).

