7.2 Follow-up Procedure

A prospective observation will be done for a period of one month after completion of the trial (6 months) by both groups. The drug intervention will be withdrawn in the drug group and LSM group will be on normal life style to measure the efficacy of the trial drug and LSM in both the groups. A comparison (physical assessment and blood sugar (OGTT) between the trial and non-trial period will be drawn in the outcome.

8. Safety and Efficacy Assessments

Liver function test and renal function test are recorded before and after trial drug administration to measure the safety of the drug. OGTT, HbA1c and blood glucose levels also measured for efficacy of the drug. Lipid profile is tested to measure the complementary benefit of the drug in microvascular end arterial diseases.

9. Adverse Event Reporting

If any adverse drug reaction or adverse event is reported, the study subject will be referred to the Pharmacovigilance cell of the study centre. According to the advice of the Pharmacovigilance cell withdrawal or continuation of the study will be determined.

10. Statistical Methods/Data Analysis

All the data will be entered in the Microsoft excel and the data will be analyzed using SPSS Version 16. Quantitative data shall be given in mean and standard deviation. Prevalence

shall be given in proportion with 95% confidence interval. Association with risk factors shall be analyzed using chi square test and multivariate analysis. Correlation shall be analyzed using Karl Pearson, with significant level ($P < 0.005$ or $P < 0.05$). Comparison between means with Annovatest, difference between means assessed by paired t test. Further analysis will be extended depending upon the results at the end of the study.

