8. The Diabetes prevention program (DPP) Research Group. *Diabetes care*, 2002, 25:2165-2171.

**OPEN LABELED RANDOMIZED CONTROLLED CLINICAL TRIAL ON
IMPAIRED GLUCOSE TOLERANCE –IGT (Munneerizhivu)**

FORM I - SCREENING PROFORMA

1. Code No (of clinical trial)
2. Centre: _____
3. Name of the Patient _____
4. S. No. of Patient _____
5. Gender Male (1) Female (2)
6. Date of Birth Age (Years)
7. Address _____

Mobile:

Phone no:

CRITERIA FOR INCLUSION

Yes (1)

No (0)

- | | | |
|---|----------------------|----------------------|
| 8. Age between 30 years and 60 years |  |  |
| 9. OGTT – After 2 hours < 140 mg and > 199 mg |  |  |
| 10. Glycated hemoglobin (HBA1C) >6.0% and <6.5% |  |  |

11. Blood sugar – Fasting > 100 and =< 125 mg/dl

CRITERIA FOR EXCLUSION

12. Age below 30 and above 60 years.

13. Malignant and accelerated hypertensive

14. CVS disorder (CAD)

15. Pregnant woman or the women planning to be pregnant in next six months

16. Lactating mothers

17. Secondary Diabetes mellitus

18. Patient undergoing regular treatment for Diabetes or for any other severe illness

19. CNS disorder e.g. encephalopathy

If yes to S.No.8-11 admit the patient into the study.

If admitted subject _____ No. _____

Date: _____

Signature of the Doctor _____

**OPEN LABELED RANDOMIZED CONTROLLED CLINICAL TRIAL ON
IMPAIRED GLUCOSE TOLERANCE –IGT (Munneerizhivu)**

FORM I A – SELECTION PROFORMA

1. Code No. (Clinical trial)
2. Centre :
3. Name of the Patient _____
4. S. No. of Patient _____
5. Gender Male (1) Female (2)
6. Date of Birth Age (Years)
7. Address _____

8. Educational status
Illiterate (1) Read & Write (2)
Educational qualifications _____ (3)
9. Occupation
Desk Work (1) Field Work (2) Others Specify _____
10. Income per capita per month in ₹ _____

Chief complaint with duration (if any) in days (mostly asymptomatic)

- | | Absent (0) | Present (1) |
|------------------------------------|----------------------|----------------------|
| 11. Polyuria (Excessive Urine) |  |  |
| If present, duration in days _____ | | |
| 12. Polyphagia (Excessive Hunger) |  |  |
| If present, duration in days _____ | | |
| 13. Polydipsia(Excessive Thirst) |  |  |
| If present, duration in days _____ | | |

Absent (0)

Present (1)

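### The only safety endpoint is normal liver and renal tests, so adverse events cannot count against the drug and unchanged entry abnormalities can

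*Protocol*

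**What the plan says.** The secondary objective (section 2.2) is "To determine the Toxicological data of Siddha formulation". Section 8 names the safety measurements: "Liver function test and renal function test are recorded before and after trial drug administration to measure the safety of the drug". Section 10.1.2, the only entry under secondary endpoints, turns these into a success rule: "Normal Liver function test and renal function test should be taken as success end point towards safety". It does not name the analytes, the limits of normal, the visit or the day-0 value.

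Adverse events appear in section 9: "If any adverse drug reaction or adverse event is reported, the study subject will be referred to the Pharmacovigilance cell of the study centre". The stated consequence concerns the individual's participation: "According to the advice of the Pharmacovigilance cell withdrawal or continuation of the study will be determined". Section 6.1.1 adds withdrawal for a serious complication, with the probable cause noted. Section 10 names no adverse event summary.

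Form II, for the monthly visits, lists five complaints (polyuria, polyphagia, polydipsia, tiredness, body ache), vital signs and physical signs such as jaundice and oedema. It has no adverse event item. Form III schedules the full laboratory panel at days 0, 90 and 180.

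Section 5.1 excludes "Chronic Liver and Renal diseases" but sets no laboratory limit. The exclusion list on Form I (items 12 to 19) does not name liver or renal disease, and the form's admission instruction is "If yes to S.No.8-11 admit the patient into the study", which are the age and glycaemia items.

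**The concern.** A safety endpoint should register harm when it occurs and should not register what was there before treatment. This one falls short on both counts.

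- **Harm outside the liver and kidney does not register.** A reaction that leaves the liver and renal tests normal is referred and managed, but does not alter the endpoint.
- **Pre-existing abnormality does register.** The rule looks at whether a test is normal, not at whether it changed. A value out of range at day 0 and still the same at day 180 counts against safety.

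At stake is the trial's one stated safety conclusion. It could be favourable despite adverse events, or unfavourable for reasons unrelated to the drug. The primary endpoint is not affected.

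**Working it through.** The plan attaches no figure to this endpoint, so there is none to reproduce. The only design figure is 30 per group, 60 in total (section 10.2). The defect follows from the text; the arithmetic only shows why no single chance-failure rate can be claimed.

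**1. Does any route carry an adverse event into the endpoint?**

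| Place | What it does with an adverse event | Feeds 10.1.2? |
|---|---|---|
| Section 9 | Referral, then advice on withdrawal or continuation | No |
| Section 6.1.1 | Withdrawal, probable cause noted | No |
| Form II | Listed complaints and signs, no adverse event item | No |
| Section 10 | No adverse event summary named | No |

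An arm's result on 10.1.2 can therefore be 30/30 at any adverse event count from 0 to 30.

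**2. Is day 0 used?** Form III supplies it; 10.1.2 does not refer to it. If an assumed 5% to 20% enter with an out-of-range value that persists, then 30 × 0.05 = 1.5 to 30 × 0.20 = 6 participants per arm count against safety without any drug effect.

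**3. How many unaffected people would fail by chance?** Form III has nine items under the liver heading (39 to 47) plus urea, creatinine and uric acid (31 to 33), 12 in all. Section 10.1.2 does not say which count. Assume that each reference range covers the central 95% of healthy people and that one visit is judged.

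- Independent items, both directions: 1 − 0.95^12 = 1 − 0.540 = 46.0%.
- Independent items, high values only: 1 − 0.975^12 = 1 − 0.738 = 26.2%.
- Equal correlation ρ between items, c = 1.96: P(all k in range) = ∫ [Φ((c − √ρ z)/√(1 − ρ)) − Φ((−c − √ρ z)/√(1 − ρ))]^k φ(z) dz. For high values only, drop the second Φ term.

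| Analytes assumed to count | Both directions, ρ = 0 to 0.7 | High only, ρ = 0 to 0.7 |
|---|---|---|
| 2 | 9.8% to 8.4% | 4.9% to 4.2% |
| 5 | 22.6% to 14.8% | 11.9% to 7.4% |
| 12 | 46.0% to 23.2% | 26.2% to 11.6% |

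The range runs from about 4% to 46%, depending on choices the protocol does not state.

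**4. Would counting new abnormalities be enough?** Simulating 12 items with two-sided limits, ρ = 0 to 0.7 and an assumed within-person correlation of 0.5 to 0.8, about 13% to 41% of unaffected people who are normal at day 0 show at least one out-of-range value at a single later visit. Replacing normal by newly abnormal, with no threshold set in advance, leaves much of the noise in place.

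**5. What can 30 per arm show?** With 0 events in 30, the one-sided 95% upper limit is 1 − 0.05^(1/30) = 9.5%, and the upper end of the two-sided 95% interval is 1 − 0.025^(1/30) = 11.6%. This reflects the sample size and holds under any endpoint wording.

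**The case against.** The strongest reply is that the trial records more than 10.1.2 uses. Section 10 provides means and standard deviations, paired t tests, comparison of means and proportions with 95% confidence intervals. Form III collects the panel at days 0, 90 and 180 with no restriction to one arm. Form II records symptoms and signs each month. Adverse event tables by arm are commonly left to a statistical analysis plan, which may exist here. Section 5.1 excludes chronic liver and renal disease, and randomization balances entry and chance abnormalities on average.

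Much of this stands, and it rules out several stronger readings that a reader might infer:

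- *The secondary objective cannot be answered, or the arms cannot be compared.* Not supported: laboratory comparisons, including with day 0, are available under section 10.
- *Symptomatic harm disappears.* Too strong: events are referred and managed, and Form II captures some symptoms and signs. They are absent from the endpoint, not from the trial.
- *23% to 46% of unaffected participants would fail.* This needs all 12 items to be normal in both directions, which the protocol does not say. Some items are derived from others (globulin and the A/G ratio), and high values only gives about 12% to 26%.
- *A participant withdrawn for a reaction is scored a success.* Scoring per participant is the natural reading but is not stated, and neither is a test after withdrawal.
- *Chronic liver or renal disease is admitted.* Section 5.1 excludes it; the gap is that Form I does not carry the exclusion and no laboratory limit is set.

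What the reply does not remove is the rule itself. An analysis plan may add tables, but the protocol would still define safety success by normal tests alone. Randomization cannot restore adverse events that never enter the endpoint.

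**Conclusion.** The point holds as a badly stated rule in section 10.1.2. As written, the drug can be declared a safety success whatever its adverse events, and an abnormality present at entry and unchanged counts against safety although its day-0 value is on file. Both conclusions rest on the text alone. They apply whether success is judged per participant or per group.

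The amount of chance failure is not fixed by the documents. The 4% to 46% span rests on assumed reference ranges, correlations and analyte lists, and no single percentage from it should be quoted. On average chance failures fall on both randomized arms alike, so they add noise to a comparison between arms and do not bias it against the drug.

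This is a worthwhile, cheap improvement to one secondary endpoint of a trial that section 10.2 describes as exploratory.

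**What to change.** Reword section 10.1.2 so that safety is reported by arm as:

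- **(a) Adverse events.** The number and percentage of participants with any adverse event, any serious adverse event and any event leading to withdrawal, with exact 95% confidence intervals. Collect these through one adverse event line on Form II at each monthly visit in both arms, alongside the section 9 reports.
- **(b) Laboratory safety.** Change from day 0 to days 90 and 180 in named liver and renal analytes, plus shifts from baseline beyond a threshold that the sponsor sets in advance, compared between arms.

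Remove the rule that normal tests alone are a safety success. Carry the section 5.1 liver and renal exclusion onto Form I so that the two agree.

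The cost is a change of wording, one line on Form II and one item on Form I. The visits and tests are already planned. The downside is a safety statement that may look less favourable, with intervals that show how little 30 per arm can exclude.

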10.2 Sample size determination

60 is the sample size as per the phase (Exploratory trial) of the clinical trial. 30 subjects will be enrolled in each group.

11. Criteria for Success of Treatment

Prevention or non-transformation of IGT to full blown diabetes which is measured by the primary end point will be considered as criteria stated above.

12. Trial Monitoring and Data Analyses

The progress of the trial will be monitored by the Guide. Data analysis will be done by the investigator.

13. Ethical Review

Institutional Ethical Committee (IEC) of participating centre is sought for clearance certificate before the project is initiated. Patient's information sheet and informed consent form will be submitted (Regional Language - Tamil) along with project proposal for approval by IEC. Both will be maintained in duplicate. Consent form will be given to the subject and will be enrolled with proper consent. One copy of Patient Information Sheet (PIS) will be given to the patient at the time of entry to the trial.

Reference:

1. Shukla s.s et al fundamental aspects and basic concepts of Siddha medicines. SYST-Re pharm 2011; 2:48-54.
3. American Diabetes Association. Diagnosis and classification of diabetes mellitus. *Diabetes Care*.2010; 33:S62–S69.
4. Unwin N et al, Impaired glucose tolerance and impaired fasting glycaemia: the current status on definition and intervention. *Diabet Med*. 2002; 19:708–723.
5. International Expert Committee. International Expert Committee report on the role of the A1C assay in the diagnosis of diabetes. *Diabetes Care*. 2009; 32:1327–1334.
6. Anjana RM et al, Prevalence of diabetes and prediabetes (impaired fasting glucose and/or impaired glucose tolerance) in urban and rural India: Phase I results of the Indian Council of medical research-India Diabetes (ICMR-INDIAB) study, 2011, *Diabetologia*, 54:3022-7.
7. Diagnosis, Prognosis, and Treatment of Impaired Glucose Tolerance and Impaired Fasting Glucose, McMaster University Evidence-based Practice Center, Hamilton, Ontario, Canada
<http://archive.ahrq.gov/downloads/pub/evidence/pdf/impglucose/impglucose.pdf>

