41. SGOT (IU/L) _____

- 42. SGPT (IU/L) _____
- 43. Alk. Phosphatase (KA units) _____
- 44. Total proteins (gm/dl) _____
- 45. Albumin (gm/dl) _____
- 46. Globulin (gm/dl) _____
- 47. A/G Ratio _____

Serum Electrolytes

- 48. Sodium (mEq/L) _____
- 49. Potassium (mEq/L) _____
- 50. Chloride (mEq/L) _____

Sl.No.10-50 will be done during I visit (0 day), IV visit (90th day) and VII visit (180th day).

Sl.No.28 & 29 (Blood Sugar- F & PP) in the following visits II, III, V and VI.

Date:

--	--

--	--

--	--

Signature of Investigator/ Medical Officer

**OPEN LABELED RANDOMIZED CONTROLLED CLINICAL TRIAL ON
IMPAIRED GLUCOSE TOLERANCE –IGT (Munneerizhivu)**

**FORM II - CLINICAL & PHYSIOLOGICAL ASSESSMENT
[Before Treatment & During monthly visit]**

1 st visit – 0 day		5 th visit – 120 th day	
2 nd visit – 30 th day		6 th visit – 150 th day	
3 rd visit – 60 th day		7 th visit – 180 th day	
4 th visit – 90 th day		8 th visit – 210 th day	

1. Code No. (Clinical trial)
2. Centre : Siddha Central Research Institute, Arumbakkam, Chennai.
3. Name of the Patient _____
4. S. No. of Patient _____
5. Gender Male (1) Female (2)
6. Date of Birth Age (Years)
7. Address _____

Chief complaint with duration (if any) in days (mostly asymptomatic)

- | | Absent (0) | Present (1) |
|------------------------------------|---|---|
| 8. Polyuria (Excessive Urine) |  |  |
| If present, duration in days _____ | | |
| 9. Polyphagia (Excessive Hunger) |  |  |
| If present, duration in days _____ | | |
| 10. Polydipsia(Excessive Thirst) |  |  |

If present, duration in days _____

11. Exhaustion/Tiredness

If present, duration in days _____

Absent (0)

Present (1)

12. Body ache

If present, duration in days _____

VITAL SIGNS

13. Pulse rate/min

14. Heart rate/min

15. BP(mm of Hg)

 /

16. Temperature °F

 .

PRESENT(1)

ABSENT (2)

17. Cyanosis

18. Anaemia

19. Jaundice

20. Clubbing

21. Lymphadenopathy

22. Oedema

23. Height/cm

 .

24. Weight/Kgs

 .

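### Section 10.1.2 counts normal liver and renal tests as safety success, but about 30 exposed people and a rule with no rate, bound, baseline or comparison cannot support a conclusion of safety

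*Protocol*

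**What the plan says.** The secondary objective (Protocol, 2.2) is "To determine the Toxicological data of Siddha formulation". The endpoint that serves it (10.1.2) is one sentence: "Normal Liver function test and renal function test should be taken as success end point towards safety". That section contains nothing else.

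The exposed group follows from two places. Under Study Design (section 3), "To one group is assigned life style modification and test drug", and the other group has lifestyle modification alone. Section 10.2 states "30 subjects will be enrolled in each group" and gives the basis of the total: "60 is the sample size as per the phase (Exploratory trial) of the clinical trial". Section 6 sets the exposure: "Duration of the medication: 180 days".

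On measurement, section 8 says "Liver function test and renal function test are recorded before and after trial drug administration to measure the safety of the drug". The note at the end of Form III adds a middle time point: "Sl.No.10-50 will be done during I visit (0 day), IV visit (90th day) and VII visit (180th day". Those item numbers include the renal and liver tests, and the note is not restricted to one arm.

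Section 10 plans proportions with 95% confidence intervals, but only for what it calls prevalence, and does not connect them to 10.1.2. Section 9 sends individual adverse events to the pharmacovigilance cell; they play no part in the success rule.

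**The concern.** An endpoint worded as success when tests are normal treats the absence of a finding as a finding. In about 30 exposed people, absence is expected quite often even if the drug does affect the liver or kidney in a few per cent of users. The sentence states no rate still compatible with the data and sets no tolerable rate. It also does not say what is normal, at which visit, or relative to what. It looks neither at the participant's own day-0 value nor at the lifestyle-only arm, which is the one feature of the design that could separate drug effects from incidental abnormality.

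At stake is the trial's only secondary objective. A report that follows 10.1.2 as written could present a clean laboratory record as a positive result on toxicology without evidence to bear it. It could equally record a failure because of incidental abnormal values.

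**Working it through.** **The plan's own figure.** 30 + 30 = 60, which agrees with section 10.2. No event rate, margin, power or dropout is given as its basis, so nothing further can be reproduced.

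**Inputs.** Exposed number n = 30 (sections 3 and 10.2). Confidence level 95%, the level named in section 10, though not for this endpoint. Reading of the rule: all 30 normal. This is the strictest group reading; one based on means or on most patients would be no harder to pass.

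**Step 1: what a clean record leaves open.** With 0 events in n, the exact upper limit is 1 − 0.025^(1/n) two-sided and 1 − 0.05^(1/n) one-sided.

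- n = 30, two-sided: 1 − 0.025^(1/30) = 0.1157, or 11.6% (1 in 8.6).
- n = 30, one-sided: 1 − 0.05^(1/30) = 0.0950, or 9.5% (1 in 10.5).
- Two approximations as a check: rule of three, 3/30 = 10.0%; Wilson, 11.35%.
- If fewer were evaluable (an assumption, since no dropout is stated): n = 27 gives 12.8% and n = 24 gives 14.2%, both two-sided.

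**Step 2: how often the rule is passed at a given true rate.** With true rate p of liver or renal abnormality and no background abnormality, P(0 of 30) = (1 − p)^30. The protocol gives no rates, so these are assumed.

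| Assumed true rate | P(clean record in 30) |
|---|---|
| 1% | 0.99^30 = 0.740 |
| 2% | 0.98^30 = 0.545 |
| 3% | 0.97^30 = 0.401 |
| 5% | 0.95^30 = 0.215 |
| 10% | 0.90^30 = 0.042 |
| 11.57% | 0.8843^30 = 0.025 |

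**Step 3: incidental abnormality.** Suppose instead that the drug is harmless and 5% of participants have an incidental abnormal result (assumed). The chance of passing is again 0.95^30 = 0.215, so the harmless drug fails 1 − 0.215 = 0.785 of the time. The rule returns the same answer whether the 5% comes from the drug or from background. If the drug added an independent 2% to that background, the chance of passing would be 0.2146 × 0.5455 = 0.117. A harmless drug and one affecting 2% of users would thus pass 21% and 12% of the time, which is little separation.

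**Step 4: scale.** A clean record would exclude a 5% rate only with 72 exposed (two-sided) or 59 (one-sided), and a 1% rate only with 368 or 299. These figures show what 30 can carry; they are not a request for more patients.

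**The case against.** The strongest reply is that the rule has been read into the text. The wording is *towards* safety, and the parallel sentence on the primary endpoint (10.1.1) classifies an outcome of treatment in a way that reads naturally per patient. Read so, 10.1.2 defines a patient-level result and no group verdict exists. This stands in part. A reader might infer that the protocol will declare a toxic drug safe, but the document does not say so. What remains is that the endpoint carries a success label, does not state its level, and offers no other route from the tests to the toxicology objective.

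A reader might also infer that the trial would miss harm in about one user in nine. It would not: at a true rate of 11.6% a clean record has only a 2.5% chance. That figure is the edge of a confidence interval. The range realistically missed is roughly 1% to 5%. Nor is an abnormal test the same as harm; the bound covers only liver and renal results at the scheduled visits.

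The trial is exploratory, and any arm of 30 has such a limit. That is correct, and the sample size is not the fault. A small sample is a reason to estimate rather than to label a result as success.

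Tabulation by arm can be left to a statistical analysis plan, and intervals are not foreign to section 10. But the success criterion is fixed in the protocol, and an analysis plan faithful to it would inherit the problem. Other safety data exist too (adverse events, haematology, electrolytes, urine), but none enters the stated endpoint.

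Finally, with background abnormality the rule may be too strict rather than too lax. This also stands: the direction of error is not established.

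**Conclusion.** The point holds as a fault in the endpoint's wording. Normal liver and renal tests in about 30 exposed people cannot support a conclusion of safety: a fully clean record is compatible, at 95% confidence, with abnormality rates up to 11.6% (9.5% one-sided), and would arise 74%, 55% and 21% of the time at assumed true rates of 1%, 2% and 5%. Without a day-0 reference and a comparison between arms, the rule also cannot attribute abnormal results to the drug, so it may err either way.

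This rests on the strict reading (all 30 normal), on all 30 being evaluable and, for the 74%, 55% and 21%, on no background abnormality. The protocol supplies no background rate, tolerable rate or dropout. It does not follow that the trial is too small for its exploratory purpose or that the sponsor intends to claim proven safety.

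**What to change.** Replace the success wording in 10.1.2 with:

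> The number and proportion of participants in each arm with a liver or renal result that is normal at day 0 and outside the laboratory's reference range at day 90 or 180 will be reported with exact 95% confidence intervals, together with the difference between arms. The absence of abnormal results will not be taken as showing safety.

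This defines abnormal, fixes the visits, uses the baseline value and the lifestyle-only arm, and puts the remaining uncertainty on the page. Section 8 should be aligned with the Form III note, because section 8 names only before and after treatment.

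Cost: no extra patients, visits or tests, provided Form III is completed in both arms, as its unrestricted note implies. The safety statement becomes less favourable. The comparison between arms will be descriptive: with 0 of 30 abnormal in the lifestyle-only arm, 5 of 30 in the drug arm gives a two-sided Fisher p of 0.052 and 6 of 30 gives 0.024, so no test should be made the new success rule.

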7.1 Screening procedures

The full details of history, physical examination, anthropometric measurements, 24-hours diet recall, physical activity of the patients will be recorded as per the proforma. OGTT is the critical investigation for this study and based on this the screening will be done. Investigations - HbA1c and Fasting blood sugar, Lipid profile, Liver function test, Renal function test, Electrolytes and Urine analysis will be taken before and after treatment and the reports will be recorded.

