39. BMI

Date:

Signature of Investigator/ Medical Officer

**OPEN LABELED RANDOMIZED CONTROLLED CLINICAL TRIAL ON
IMPAIRED GLUCOSE TOLERANCE –IGT (Munneerizhivu)**

FORM III - LABORATORY INVESTIGATIONS (Before Treatment – 0 day)

1. Code No. (of clinical trial)
1. Centre: Siddha central Research Institute, Arumbakkam, Chennai.
3. S. No. of Patient _____
4. Name of the Patient _____
5. Address _____

6. Gender Male (1) Female (2)
7. Date of Birth 8. Age (Years)
9. Date of Assessment

**Urine Examination
Routine**

10. Sugar _____ 11.a) Albumin _____ b) Microalbumin _____
12. Deposits _____

Microscopic

13. Pus cell _____ (HPF)

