14. RBC _____ (HPF)
15. Cast _____ (HPF)

Stool examination

16. Routine _____

Microscopic

17. Ova _____ 18. Cyst _____ 19. Occult Blood _____

Blood

20. TC (Cells/Cumm) _____

Differential Count

21. P (%) _____ 22. L (%) _____ 23. E (%) _____ 24. M (%) _____ 25. B (%) _____

26. Hb (g/dl) _____.

27. ESR (1/2 hour.) _____ ESR (1 hour.) _____

28. Blood Sugar- Fasting (mg/dl) _____

29. Blood Sugar – OGTT (mg/dl) _____ (After 2 hours)/ PP _____ (mg/dl)

30. Glycated Hemoglobin (HbA1c) _____ (to be done before treatment and at the end of treatment)

31. Blood Urea (mg/dl) _____

32. S. Creatinine (mg/dl) _____

33. Uric acid (mg/dl) _____

LIPID PROFILE

34. Serum total Cholesterol (mg/dl) _____

35. S. Triglycerides (mg/dl) _____

36. HDL (mg/dl) _____

37. LDL (mg/dl) _____

38. VLDL (mg/dl) _____

LIVER FUNCTION TEST

Serum Bilirubin

39. Total (mg/dl) _____

40. Direct (mg/dl) _____

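### The safety success endpoint rests on liver and renal tests only, which is narrower than the toxicology objective and than the laboratory panel the trial already collects

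*Protocol*

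**What the plan says.** The secondary objective (Protocol Section 2.2) is broad: "To determine the Toxicological data of Siddha formulation". It is not restricted to any organ system.

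The safety endpoint (Section 10.1.2) is: "Normal Liver function test and renal function test should be taken as success end point towards safety". Section 8 agrees with it: "Liver function test and renal function test are recorded before and after trial drug administration to measure the safety of the drug". No other test is tied to safety in the text.

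Section 7.1 gives a longer list of investigations: "Liver function test, Renal function test, Electrolytes and Urine analysis will be taken before and after treatment". Here electrolytes and urine analysis stand beside the renal function test as separate entries.

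Form III is wider again. It has urine items including "b) Microalbumin", stool items including "19. Occult Blood", blood count, haemoglobin and ESR, and electrolytes. Its footer fixes the schedule: "Sl.No.10-50 will be done during I visit (0 day), IV visit (90th day) and VII visit (180th day".

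Two other sections bear on the point. Section 9 refers a participant with a reported adverse event or drug reaction to the pharmacovigilance cell, which advises on withdrawal or continuation. Section 10 has all data entered and analysed, with quantitative data given as mean and standard deviation.

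**The concern.** The protocol is not silent on safety. It states a success rule, and the rule is narrower than the objective it serves. A participant whose haemoglobin falls, or whose stool becomes positive for occult blood, meets the success wording provided the liver and renal tests are normal.

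At stake is what the trial may claim on objective 2.2. A report that most participants were safety successes would read as a general statement on toxicity, although the criterion looked at two organ systems while results for others had been collected under the same schedule.

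**Working it through.** No figure in the plan needs reproducing. The check sets the endpoint against the form, item by item.

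**1. What can enter the endpoint.** Form III has a liver function heading (items 39-47). It has no renal function heading. Urea, creatinine and uric acid (31-33) are the natural candidates, but the protocol never lists what its renal function test contains.

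**2. What is clearly outside.** No reading of liver or renal function test takes in:
- total count, differential count, haemoglobin and ESR: items 20-27, 8 items;
- stool occult blood: item 19, 1 item.

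Subtotal 8 + 1 = 9. The blood count appears only on the form; no section of the text mentions it.

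**3. What is probably outside.**
- urine albumin and microalbumin, deposits, pus cells, red cells and casts: items 11-15, 5 items;
- sodium, potassium and chloride: items 48-50, 3 items.

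Subtotal 5 + 3 = 8. The evidence is the list in Section 7.1 ("Renal function test, Electrolytes and Urine analysis will be taken before and after treatment"), which treats these as different from the renal function test. That is good evidence of intent but not a definition.

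**4. Total.** 9 + 8 = 17 numbered items relevant to toxicity and scheduled at days 0, 90 and 180. Urine sugar (10) is left out of the count as a glycaemic measure. Routine stool, ova and cyst (16-18) are left out because they say little about drug toxicity.

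**5. Whether another section changes the classification.**

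| Section | What it does with such a result | Effect on the 10.1.2 classification |
|---|---|---|
| 8 | Names liver and renal tests for safety | None |
| 9 | Acts on a reported adverse event; does not say whether a laboratory abnormality is one | None |
| 10 | Enters and analyses all data; mean and SD for quantitative items | None |

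A group mean can also stay close to its starting value when a few of 30 participants shift out of range, and mean and SD do not suit a positive or negative result such as occult blood.

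**6. Chance abnormalities if the items are added.** Assume, for illustration, that each item has a 95% reference range and that items are independent. The chance that a healthy person has at least one item out of range at one visit is 1 - 0.95^k:
- k = 9: 1 - 0.630 = 0.37;
- k = 17: 1 - 0.418 = 0.58.

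Per item and visit, the expected chance count in an arm of 30 is at most 30 × 0.05 = 1.5. Such findings are expected equally in both arms, so the lifestyle (LSM) arm is the yardstick. Correlated items, or items without a 95% range, would change these figures.

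**The case against.** The strongest reply is that nothing is hidden. Section 10 analyses all data, haemoglobin, counts and electrolytes are quantitative and so will be summarised, and Section 9 gives a route for adverse events. Nothing says objective 2.2 is to be judged only through Section 10.1.2. This stands against a stronger inference that a reader might draw: that abnormal blood counts or occult blood cannot count against the drug at all, or that the conclusion on toxicity must be wrong. The documents do not support that. It does not answer the narrower point, because neither section alters who is a safety success.

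A second reply is that the renal function test is never itemised, so urine protein or electrolytes could be read into it. This stands in part, and is why those eight items are called only probably outside. It leaves blood count and occult blood where they are.

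A third reply is that laboratory shift tables belong in a statistical analysis plan, which is not shown. That is fair as to table layout, and no fault is found with the absence of tables. A stated success criterion is protocol content, and an analysis plan would normally carry it out rather than replace it.

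Finally, this is one secondary endpoint in a 60-person trial described as exploratory, and a focus on liver and kidney may be deliberate. If so, the safety claim should be worded to match.

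**Conclusion.** The point holds in limited form. The safety success rule covers liver and renal tests, the objective covers toxicity in general, and 17 scheduled Form III items relevant to toxicity (9 clearly, 8 probably) lie outside the rule. A participant with an isolated abnormality there is classed as a safety success.

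This rests on reading Section 10.1.2 as written and, for urine and electrolytes, on the separate listing in Section 7.1. The protocol gives no rates for such abnormalities, so the number of participants affected cannot be estimated. It does not follow that the data would be ignored or that the drug would wrongly be declared safe. It is a cheap improvement in wording and reporting, not a threat to the trial's main result.

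**What to change.** In Sections 8 and 10.1.2:

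1. State which Form III items make up the renal function test.
2. Add items 11-15, 19, 20-27 and 48-50 to the safety result. For each, give by arm the number of participants normal at day 0 who are outside the laboratory's range at day 90 or day 180, with the number assessed. Keep this descriptive and read it against the LSM arm.
3. If the endpoint is to stay as it is, limit the safety conclusion to liver and renal function and say so.

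The cost is a wording change and a few extra tables. No new test or visit is needed, provided Form III is completed in both arms; the form itself carries no restriction by arm, but the text should confirm it. The downside is more chance abnormalities to interpret, which is why the comparison arm matters and why the counts should not be turned into tests.
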